8.5.1.2 Unsolicited Adverse Events

All AEs spontaneously reported by the subject and/or in response to an open question from study personnel or revealed by observation, physical examination or other diagnostic procedures must be recorded in the source document and on the appropriate page of the case report form. All reported unsolicited AEs are graded in accordance with the protocol toxicity tables.

8.5.1.3 Unexpected

An adverse reaction, the nature or severity of which is not consistent with the applicable product information (e.g., investigator’s brochure for an unapproved investigational medicinal product).

8.5.2 Definition of Serious Adverse Events (SAE)

An adverse event or suspected adverse reaction is considered "serious" if, in the view of either the investigator or sponsor, it results in any of the following outcomes (21 CFR 312.32 (a)):

- Death.
- A life-threatening adverse event.
- Inpatient hospitalization or prolongation of existing hospitalization.
- A persistent or significant incapacity or substantial disruption of the ability to conduct normal life functions, or
- A congenital anomaly/birth defect.

Important medical events that may not result in death, be life-threatening, or require hospitalization may be considered serious when, based upon appropriate medical judgment, they may jeopardize the patient or subject and may require medical or surgical intervention to prevent one of the outcomes listed in this definition. Examples of such medical events include allergic bronchospasm requiring intensive treatment in an emergency room or at home, convulsions that do not result in inpatient hospitalization, etc.

SAEs will be:

- Assessed for severity and relationship to study product and alternate etiology (if not related to study product) by a licensed study physician listed on the FDA Form 1572 or by the Institution as the site Principal Investigator or Sub-Investigator.
- Recorded on the appropriate SAE data collection form and eCRF.
- Followed through resolution by a licensed study physician (for investigational new drug application [IND] studies, a physician listed on the FDA Form 1572 as the site Principal Investigator or Sub-Investigator).

Reviewed and evaluated by the sponsor, the Safety Monitoring Committee (SMC) (periodic review unless related), and the IRB/IEC.

8.5.2.1 Suspected Unexpected Serious Adverse Reactions (SUSAR)

A SUSAR is any SAE where a causal relationship with the study product is at least reasonably possible but is not listed in the Investigator Brochure, Package Insert, and/or Summary of Product Characteristics.

8.5.3 Classification of an Adverse Events

The determination of seriousness, severity, and causality will be made by an on-site investigator who is qualified (licensed) to diagnose, provide a medical evaluation of adverse events, and classify adverse events based upon medical judgment. This includes but is not limited to physicians, physician assistants, and nurse practitioners.

8.5.3.1 Seriousness and Severity of Event

Event seriousness will be determined according to the protocol definition of an SAE (Section [8.5.1](#)). All AEs or SAEs will be assessed for severity, according to the toxicity grading scales in [Appendix A](#).

For adverse events (AEs) not included in the protocol defined grading system, the following guidelines will be used to describe severity.

- Mild (Grade 1): Events that are usually transient and may require only minimal or no treatment or therapeutic intervention and generally do not interfere with the subject's usual activities of daily living.
- Moderate (Grade 2): Events that are usually alleviated with additional specific therapeutic intervention. The event interferes with usual activities of daily living, causing discomfort but poses no significant or permanent risk of harm to the research participant.
- Severe (Grade 3): Events interrupt usual activities of daily living, or significantly affects clinical status, or may require intensive therapeutic intervention. Severe events are usually incapacitating.

8.5.3.2 Relationship to Study Intervention

The licensed study physician's assessment of an AE's relationship to study product is part of the documentation process, but it is not a factor in determining what is or is not reported in this study. If there is any doubt as to whether a clinical observation is an AE, the event should be reported. The relationship to study product must be assessed for AEs using the terms: related or not related. In general, the study product must always be suspect. To help assess, the following guidelines are used:

- Related – The AE is known to occur with the study intervention, there is a reasonable possibility that the study intervention caused the AE, or there is a temporal relationship between the study intervention and event. Reasonable possibility means that there is evidence to suggest a causal relationship between the study intervention and the AE.
- Not Related – There is not a reasonable possibility that the administration of the study intervention caused the event, there is no temporal relationship between the study intervention and event onset, or an alternate etiology has been established.

8.5.4 Time Period and Frequency for Event Assessment and Follow-up

For this study all solicited AEs will be documented for the 8 days following study product administration.

For this study, all unsolicited, non-serious AEs will be documented from Study Visit 01 (Day 1) through Study Visit 07 (Day 29 post second vaccination).

All MAAEs, SAEs and new onset chronic medical conditions (NOCMC) will be documented from Study Visit 01 (Day 1) through Study Visit 09 (final visit).

Resolution of an AE is defined as the return to pre-treatment status or as stabilization of the condition, with the expectation that it will remain chronic. Site PIs are required to follow all reported AEs until either resolution of the AE or until the event is stable, as determined by the site PI; all SAEs will be followed until either resolution

of the SAE or until the SAE is stable, as determined by the PI. Subjects who have an unresolved SAE at either the final study visit or at discontinuation of study participation will continue to be followed, with the subject's permission, until the SAE is stable/deemed chronic, as determined by the site PI.

8.5.5 Adverse Event Reporting

8.5.5.1 Investigators Reporting of AEs

Adverse Events, including local and systemic reactions not meeting the criteria for "serious adverse events," will be captured on the appropriate case report form. Information to be collected for unsolicited adverse events includes event description, date of onset, investigator assessment of severity, relationship to study product, date of resolution of the event, seriousness, and outcome.

8.5.6 Serious Adverse Event Reporting

8.5.6.1 Investigators Reporting of AEs

Serious adverse events will be collected throughout the study until the final visit is completed.

The following procedures will apply to all serious adverse events:

- Assessed for severity and relationship to study product and alternate etiology (if not related to study product) by a licensed physician listed on the FDA Form 1572 as the principal investigator or subinvestigator.
- Recorded on the appropriate serious adverse event report form and electronic case report form (eCRF).
- Reviewed and evaluated by an Independent Safety Monitor, the SMC (periodic review unless related), NTI and the Institutional Review Board (IRB) (as indicated).
- Reviewed and followed to resolution or stabilization by a licensed physician listed on the FDA Form 1572 as the principal investigator or subinvestigator.

The Blinded Medical Monitor will review and assess the SAE for regulatory reporting and potential impact on study subject safety and protocol conduct.

8.5.6.2 Regulatory Reporting of AEs

Following notification from the site Principal Investigator or appropriate sub-investigator, NTI, as the IND sponsor, will review the suspected unexpected serious adverse event (SUSAR) and ensure it is reported as an IND safety report to the FDA. Submissions of IND safety reports will be performed by Emmes on behalf of NTI. Emmes will notify all participating site Principal Investigators (i.e., all Principal Investigators to whom the sponsor is providing drug under its IND(s)) of potential serious risks from clinical studies or any other source, as soon as possible. Emmes, on behalf of NTI, will report to the FDA any unexpected fatal or life-threatening suspected adverse reaction as soon as possible, but in no case later than 7 calendar days after the sponsor's initial receipt of the information. If the event is not fatal or life-threatening the IND safety report will be submitted within 15 calendar days after the sponsor determines that the information qualifies for reporting as specified in 21 CFR Part 312.32. Relevant follow up information to an IND safety report will be submitted as soon as the information is available. Upon request from FDA, NTI (or Emmes, on NTI's behalf) will submit to the FDA any

additional data or information that the agency deems necessary, as soon as possible, but in no case later than 15 calendar days after receiving the request.

SAEs that are not SUSARs will be reported to the FDA at least annually in a summary format which includes all SAEs.

8.5.7 Adverse Events of Special Interest

This study will also assess New-Onset Chronic Medical Conditions (NOCMCs) from the day of receipt of the first dose of study product until study completion. NOCMCs are defined as any new ICD-10 diagnosis (10th revision of the International Statistical Classification of Diseases and Related Health Problems) that is applied to the subject during the course of the study, after receipt of the study agent, that is expected to continue for at least 3 months and requires continued health care intervention. NOCMCs will be assessed and recorded as unsolicited AEs.

8.5.8 Reporting of Pregnancy

Pregnancy is not an adverse event. Pregnancies occurring in study subjects will be reported via Advantage eClinical® on the Pregnancy Report form. No further study vaccinations will be administered to pregnant subjects, but if the subject has received a study vaccination and with the subject's permission all study mandated blood samples will be obtained and the subject will continue in follow-up for safety events. Efforts will be made to follow all pregnancies reported during the course of the study to pregnancy outcome pending the subject's permission.

8.6 Unanticipated Problems

8.6.1 Definition of Unanticipated Problems (UP)

The Department of Health and Human Services Office for Human Research Protections (OHRP) considers unanticipated problems involving risks to participants or others to include, in general, any incident, experience, or outcome that meets all of the following criteria:

- Unexpected in terms of nature, severity, or frequency given (a) the research procedures that are described in the protocol-related documents, such as the Institutional Review Board (IRB)-approved research protocol and informed consent document; and (b) the characteristics of the participant population being studied;
- Related or possibly related to participation in the research ("possibly related" means there is a reasonable possibility that the incident, experience, or outcome may have been caused by the procedures involved in the research); and
- Suggests that the research places participants or others at a greater risk of harm (including physical, psychological, economic, or social harm) than was previously known or recognized.

8.6.2 Unanticipated Problem Reporting

The investigator will report unanticipated problems (UPs) to the reviewing Institutional Review Board (IRB) and to the Coordinating Center (CC). The UP report will include the following information:

- Protocol identifying information: protocol title and number, PI's name, and the IRB project number.
- A detailed description of the event, incident, experience, or outcome.
- An explanation of the basis for determining that the event, incident, experience, or outcome represents an UP.
- A description of any changes to the protocol or other corrective actions that have been taken or are proposed in response to the UP.

To satisfy the requirement for prompt reporting, UPs will be reported using the following timeline:

- UPs that are serious adverse events (SAEs) will be reported to the IRB and to the CC/study sponsor within 24 hours of the investigator becoming aware of the event.
- Any other UP will be reported to the IRB and to the CC/study sponsor within 5 days of the investigator becoming aware of the problem.

8.6.3 Reporting Unanticipated Problems to Participants

Not applicable.

9. STATISTICAL CONSIDERATIONS

9.1 Study Hypotheses

The goal of this study is to assess the safety, reactogenicity, and tolerability of the HydroVax-002 YFV vaccine administered intramuscularly in a two-dose series at a dose of 1 mcg and at a dose of 5 mcg. Other goals are to assess YFV-specific neutralizing antibody responses after a first dose and after a second dose of HydroVax-002 YFV vaccine given at doses of 1 mcg and 5 mcg. This study, like other Phase 1 studies, is exploratory rather than confirmatory. Its purpose is to estimate event rates and patterns of immune responses rather than to test formal statistical hypotheses. For the purposes of collecting pilot data and planning of potential future trials, comparisons of secondary outcomes will be made among the groups, although the study is not powered to detect small to moderate differences.

9.2 Sample Size Considerations

A total of 25 subjects, age ≥ 18 and < 50 years of age, will be enrolled, where 10 subjects will receive 1 mcg of HydroVax-002 YFV, 10 will receive 5 mcg of HydroVax-002 YFV, and 5 will receive placebo. The study will consist of two dosing groups of HydroVax-002 YFV vaccine to be dosed sequentially. The initial dose of HydroVax-002 YFV to be evaluated in Group 1 will be 1 mcg and the next dose to be evaluated in Group 2 will be 5 mcg. The first 4 subjects of each group (3 receiving HydroVax-002 YFV and 1 receiving placebo) will serve as a sentinel subgroup. Randomization will be allocated in a 3:1 ratio between HydroVax-002 YFV and placebo in the sentinel subgroups. Subjects in each expanded subgroup will be randomized between HydroVax-002 YFV and placebo using a permuted-block design.

9.2.1 Safety

The sample size of 10 vaccinated subjects in each dosage group with 5 subjects that receive placebo is small given the early stage (Phase 1) of the product's development, thus the precision of estimate for AEs is limited. Rare adverse events are not demonstrable in a clinical study of this size, however the probabilities of observing one or more AEs given various true event rates and sample sizes are presented in [Table 8](#). If there are adverse events associated with HydroVax-002 YFV in this population, this study will have approximately 80% power to observe at least one such event in a dosage group size of 10 if the true rate is 15%. Comparisons will primarily be made between each vaccine dose group and placebo.

Table 8. Probability of observing one or more adverse events in one dosage group (n=10) given particular true event rates

“True” Unknown Event Rate	Probability of Observing an Event (%)
0.1%	1.0
0.5%	4.9
1.0%	9.6
2.0%	18.3
3.0%	26.3
4.0%	33.5

“True” Unknown Event Rate	Probability of Observing an Event (%)
5.0%	40.1
10.0%	65.1
15.0%	80.3

If there are no observed adverse events among the 10 vaccinated subjects in a dosage group associated with the investigational product, the upper 95% exact confidence bound for the incidence of adverse events will be 30.8%.

9.2.2 Immunogenicity

This study is not powered to detect small to moderate individual or pair-wise differences in immunogenicity outcomes between treatments.

9.3 Populations for Analyses

The Safety Analysis population includes all eligible subjects who received at least one dose of study vaccine.

The evaluable population includes all eligible subjects who received at least one dose of study vaccine and contributed both pre- and at least one post-study vaccination blood samples for testing for which valid results were reported.

The per protocol (PP) population excludes subjects who did not receive both doses of study vaccine or who had major protocol deviations, such as receipt of non-study vaccines during the time frame prohibited by the protocol or receipt of the second study vaccination substantially out of window.

In the case of mis-randomization subjects will be analyzed according to the study product actually received for all analysis populations.

9.4 Statistical Analyses

9.4.1 General Approach

The analyses of safety data will be primarily descriptive. Data will be represented to show difference in reactogenicity signs and symptoms between the vaccine candidate and dose groups.

9.4.2 Analysis of Primary Outcome Measures (Safety)

Solicited AEs and laboratory toxicities will be analyzed by taking the most severe response over the follow-up period, dichotomizing into a binary variable (none or mild versus moderate or severe) and using exact confidence intervals to summarize the reactogenicity and toxicity rates. Tabular and graphical summaries of events will be presented for each solicited symptom, by type (local/systemic/toxicity), severity (none or mild, moderate or severe), and time point post-vaccination.

Unsolicited AEs will be coded by the Medical Dictionary for Regulatory Activities (MedDRA) for preferred term and system organ class. The rate and exact 95% confidence intervals of AEs in aggregate, and by MedDRA categories, will be computed. SAEs will be reported by a detailed listing showing the type, MedDRA coding, relevant dates (vaccination and adverse event), severity, relatedness, and outcome for each event. Primary outcome measures include:

- Occurrence of all serious adverse events (SAEs) at any time during the study.
- Occurrence of all Grade 3 unsolicited adverse events (AEs) from first vaccination through day 29 after the second vaccination.
- Occurrence of all Grade 3 laboratory toxicities from first vaccination through day 15 after the second vaccination.
- Occurrence of solicited local AE and reactogenicity signs and symptoms in the 7 days after each vaccination.
- Occurrence of solicited systemic AE and reactogenicity signs and symptoms in the 7 days after each vaccination.
- Occurrence of any AE through day 29 after the second vaccination.

9.4.3 Analysis of Secondary and Exploratory Outcome Measures (Immunogenicity)

Basic descriptive statistics, such as point estimates and 95% confidence intervals, and graphical summaries, such as the reverse cumulative distribution, of seroconversion rates and geometric mean titer (GMT) will be computed by intervention at baseline, 15 and 29 days after the first vaccination, and 15, 29, 57, and 180 days after the second vaccination. YFV-specific neutralizing antibody titers may be measured through a standard plaque reduction neutralizing titer [PRNT₅₀] assay, or utilizing a Log₁₀ Neutralizing Index (LNI) assay [5, 38]. For the purposes of this study, and in line with recent yellow fever vaccine clinical trials [7, 8], antibody titers will be assessed using the PRNT₅₀ assay, and seroconversion will be defined as a PRNT₅₀ neutralizing antibody titer of $\geq 1:10$. The limit of detection in the neutralizing assay will be a titer of <10 . For the purposes of determining seroconversion rates and GMT, antibody titers of <10 will be assumed to be 5 (one dilution step below the assay limit value).

Rates of seroconversion will be summarized by tabulating the frequency of positive responses by treatment group at Day 29 after first vaccination and Day 57 after second vaccination. Response rates for each treatment group will be presented with their corresponding 95% confidence interval estimates at each time point. The relationship between the proportion of responders and dosage will be examined using logistic regression. The distribution of antibody titers will also be graphically summarized using the reverse cumulative frequency distribution of titers for each treatment group.

The PRNT₅₀ titers at days 15 and 29 after first vaccination and at days 15, 29, and 57 following second vaccination will be summarized graphically for each treatment group. The geometric mean titer (GMT) and pair-wise differences of each treatment group will also be presented with 95% confidence intervals. The relationship between GMT and dosage will be examined using standard linear regression methods. Secondary outcome measures include:

- Percentage of subjects achieving seroconversion ($\geq 1:10$ in plaque reduction neutralizing titer [PRNT₅₀] titer) at day 29 after first vaccination and at day 29 after second vaccination.

- Geometric mean neutralizing titers at days 15 and 29 after first vaccination and at days 15, 29, and 57 following second vaccination.
- Reverse cumulative distribution curve of neutralizing titers on Days 15 and 29 after first vaccination and at days 15, 29, and 57 after the second vaccination for each dose group and for all dose groups combined.

Exploratory outcome measures include:

- Geometric mean neutralizing titers at Day 180 following second vaccination.
- Reverse cumulative distribution curve of neutralizing titers on Day 180 after the second vaccination for each dose group and for all dose groups combined.
- Additional exploratory immunogenicity analyses utilizing the LNI assay may be conducted for comparison to historical datasets

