3. STUDY OBJECTIVES AND OUTCOME MEASURES

The overall objective of the study is to evaluate the safety and immunogenicity of two different dose levels of HydroVax-002 YFV.

OBJECTIVES	ENDPOINTS (Outcome Measures)
Primary	

To assess the safety, reactogenicity, and tolerability of the HydroVax-002 YFV vaccine administered intramuscularly in a two-dose series on Days 1 and 29 at a dose of 1 mcg or a dose of 5 mcg
	
 • Occurrence of all serious adverse events (SAEs) at any time during the study • Occurrence of all Grade 3 unsolicited adverse events (AEs) from first vaccination through Day 29 after the second vaccination • Occurrence of all Grade 3 laboratory toxicities from first vaccination through Day 15 after the second vaccination • Occurrence of solicited local AE and reactogenicity signs and symptoms in the 7 days after each vaccination • Occurrence of solicited systemic AE and reactogenicity signs and symptoms in the 7 days after each vaccination • Occurrence of any AE through Day 29 after the second vaccination
Secondary	

To assess YFV-specific neutralizing antibody responses after a first dose and after a second dose of HydroVax-002 YFV vaccine given at dose levels of 1 mcg and 5 mcg
	
 • Percentage of subjects achieving seroconversion ($\geq 1:10$ in plaque reduction neutralizing titer [PRNT₅₀] titer) at Day 29 after first vaccination and at Day 29 after second vaccination • Geometric mean neutralizing titers at Days 15 and 29 after first vaccination and at Days 15, 29, and 57 following second vaccination • Reverse cumulative distribution curve of neutralizing titers on Days 15 and 29 after first vaccination and at Days 15, 29, and 57 after the second vaccination for each dose group and for all dose groups combined
Exploratory	

To assess long-term YFV-specific neutralizing antibody responses after a second dose of HydroVax-002 YFV vaccine given at dose levels of 1 mcg and 5 mcg
	
• Geometric mean neutralizing titers at Day 180 following second vaccination• Reverse cumulative distribution curve of neutralizing titers on Day 180 after the second vaccination for each dose group and for all dose groups combined
---	--

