3.2. Endpoints

Primary Outcome Measures:

- Occurrence of all serious adverse events (SAEs) at any time during the study
- Occurrence of all Grade 3 unsolicited adverse events (AEs) from first vaccination through Day 29 after the second vaccination
- Occurrence of all Grade 3 laboratory toxicities from first vaccination through Day 15 after the second vaccination
- Occurrence of solicited local AE and reactogenicity signs and symptoms in the 7 days after each vaccination
- Occurrence of solicited systemic AE and reactogenicity signs and symptoms in the 7 days after each vaccination
- Occurrence of any AE through Day 29 after the second vaccination

Secondary Outcome Measures:

- Percentage of subjects achieving seroconversion ($\geq 1:10$ in plaque reduction neutralizing titer [PRNT₅₀] titer, at Day 29 after first vaccination and at Day 29 after second vaccination
- Geometric mean neutralizing titers at days 15 and 29 after first vaccination and at Days 15, 29, and 57 following second vaccination
- Reverse cumulative distribution curve of neutralizing titers on Days 15 and 29 after first vaccination and at Days 15, 29 and 57 after the second vaccination for each dose group and for all dose groups combined

Exploratory Outcome Measures:

- Geometric mean neutralizing titers at Day 180 following second vaccination
- Reverse cumulative distribution curve of neutralizing titers on Day 180 after the second vaccination for each dose group and for all dose groups combined

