Table 32: Number of Subjects Seroconverting for LNI Compared to PRNT₅₀ by Dose, Full Analysis Population

		PRNT ₅₀					
Population	Status by LNI	Seroconversion			No Seroconversion		
		N	%	95% CI	N	%	95% CI
Day 29 Post-Dose 1	Seroconversion	x	x.x	x.x, x.x	x	x.x	x.x, x.x
	No Seroconversion	x	x.x	x.x, x.x	x	x.x	x.x, x.x
Day 57 Post-Dose 2	Seroconversion	x	x.x	x.x, x.x	x	x.x	x.x, x.x
	No Seroconversion	x	x.x	x.x, x.x	x	x.x	x.x, x.x

Table 33: Number of Subjects Seroconverting for LNI Compared to PRNT₅₀ by Dose, Per-Protocol Population

		PRNT ₅₀					
Population	Status by LNI	Seroconversion			No Seroconversion		
		N	%	95% CI	N	%	95% CI
Day 29 Post-Dose 1	Seroconversion	X	X.X	X.X, X.X	X	X.X	X.X, X.X
	No Seroconversion	X	X.X	X.X, X.X	X	X.X	X.X, X.X
Day 57 Post-Dose 2	Seroconversion	X	X.X	X.X, X.X	X	X.X	X.X, X.X
	No Seroconversion	X	X.X	X.X, X.X	X	X.X	X.X, X.X

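### Seroconversion after dose 2 is an endpoint at Day 29, but one Protocol 9.4.3 sentence and SAP Tables 32/33 use Day 57, and no SAP table gives the PRNT50 rate with CI by group at Day 29

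*Protocol*

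**What the plan says.** **Endpoint.** Seroconversion is a PRNT50 titer of 1:10 or more (Protocol 9.4.3, SAP 3.3). Protocol 3 sets this secondary endpoint "at Day 29 after first vaccination and at Day 29 after second vaccination". The outcome list in Protocol 9.4.3 agrees ("at day 29 after first vaccination and at day 29 after second vaccination"), and so does SAP 3.2.

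**Analysis text.** Protocol 9.4.3 opens by saying that descriptive statistics, including point estimates and 95% intervals, "of seroconversion rates and geometric mean titer (GMT) will be computed by intervention at baseline", at Days 15 and 29 after dose 1, and "15, 29, 57, and 180 days after the second vaccination". That covers Day 29 after dose 2. The tabulation sentence further down names different visits: "tabulating the frequency of positive responses by treatment group at Day 29 after first vaccination and Day 57 after second vaccination". It is followed by the commitment "Response rates for each treatment group will be presented with their corresponding 95% confidence interval estimates at each time point".

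**SAP outputs.** SAP 9.1 describes GMT by group and visit (Tables 30 and 31) and mentions no seroconversion rate. SAP 9.2 says that seroconverters by either assay will be counted in Tables 32 and 33. The title of Table 32 ends "by Dose, Full Analysis Population". Both tables cross-classify PRNT50 status against LNI status, at Day 29 after dose 1 and Day 57 after dose 2 only.

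**Timing.** SAP 6.3 schedules the secondary immunogenicity outcomes for the unblinded analysis once all subjects have passed Day 57 after dose 2, and withholds individual listings until the final analysis.

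**The concern.** The protocol contradicts itself on the visit for a named secondary endpoint, and the SAP shells follow the sentence that disagrees with the endpoint. Neither the protocol amendment history nor SAP 10 records a move from Day 29 to Day 57.

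Protocol 9.4.4.2 makes the SAP the document that defines the analyses in the study report. An estimate without a planned output there has no assured place in the results. If the programmers build what is drawn, the endpoint is not tabulated by group with an interval at its own visit. That would happen at the Day 57 analysis, which SAP 2.1 says will inform a manuscript. The plan also leaves two candidate post-dose-2 visits for one endpoint, and the choice between them could be made after unblinding.

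**Working it through.** **1. Visits named for PRNT50 seroconversion after dose 2**

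| Place | Post-dose-2 visit |
|---|---|
| Protocol 3, secondary endpoint | Day 29 |
| Protocol 9.4.3, outcome list | Day 29 |
| SAP 3.2, secondary endpoint | Day 29 |
| Protocol 9.4.3, opening sentence | Days 15, 29, 57, 180 |
| Protocol 9.4.3, tabulation sentence | Day 57 |
| SAP Tables 32 and 33 | Day 57 |

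All 3 endpoint statements say Day 29; neither of the 2 seroconversion tables does.

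**2. Are the two visits interchangeable?** The Schedule of Assessments gives both a window of ±4 days. Visit 07 is 29 ± 4 = Days 25 to 33 and Visit 08 is 57 ± 4 = Days 53 to 61 after dose 2. The shortest gap is 53 − 33 = 20 days, so the windows do not overlap. Blood for neutralizing assays is drawn at both.

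**3. Which SAP outputs could carry the estimate?**

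- *Tables 30 and 31:* three groups and a Day 29 post-dose-2 row, but GMT and LNI only.
- *Tables 32 and 33:* no Day 29 post-dose-2 row. The intervals belong to the cells of the LNI-by-PRNT50 cross-table. The PRNT50 margin (the rate whatever the LNI status) has none.
- *Treatment groups in Tables 32 and 33:* none are drawn. The word dose in the titles could mean dose level or dose number, and SAP 6.1 asks for a column per treatment, so repetition by arm may be intended. Even then the visit and the margin are still missing.
- *Figures 11 to 14:* SAP 3.2 plans the reverse cumulative curves "at Days 15, 29 and 57 after the second vaccination for each dose group and for all dose groups combined". By their titles the figures cover the two vaccine doses and not placebo, and no interval is stated. The drawings themselves are not visible.
- *Listing 14:* individual titers, not produced at the Day 57 analysis.

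**4. Count of missing estimates.** Endpoint visits × groups × populations (FA and PP, the pair the SAP uses for immunogenicity) = 2 × 3 × 2 = 12. Of these, 1 × 3 × 2 = 6 (Day 29 after dose 2) have no row. The other 6 (Day 29 after dose 1) have a row but no interval on the PRNT50 margin. Per population, that is 6 estimates needed and 3 without a row.

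**5. What the missing table would hold.** The plan prints no seroconversion figure to reproduce. Its one exact bound is the 30.8% upper limit for 0/10 in Protocol 9.2.1 (safety). It reproduces as two-sided Clopper-Pearson: 1 − 0.025^(1/10) = 0.3085. Blaker's method gives 28.3% for the same count. Blaker is the only interval that the SAP names for immunogenicity, and it is attached to GMT and LNI.

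Clopper-Pearson limits for x of n are the 2.5% quantile of Beta(x, n − x + 1) and the 97.5% quantile of Beta(x + 1, n − x). Blaker limits are the ends of the set of p with acceptability of at least 0.05. The counts are illustrative; the group sizes of 10, 10 and 5 are from Protocol 9.2.

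| x/n | Clopper-Pearson 95% | Blaker 95% |
|---|---|---|
| 0/5 | 0 to 52.2% | 0 to 50.0% |
| 5/10 | 18.7 to 81.3% | 22.2 to 77.8% |
| 10/10 | 69.2 to 100% | 71.7 to 100% |

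At 5/10 the widths are 81.29 − 18.71 = 62.6 points and 77.76 − 22.24 = 55.5 points. One subject whose status differs between the visits moves a vaccine-group rate by 1/10 = 10 points and the placebo rate by 1/5 = 20 points.

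**The case against.** The endpoint visit is stated the same way in three places, and the opening sentence of Protocol 9.4.3 already promises seroconversion rates with intervals by group at every visit. On that reading the tabulation sentence only picks visits for one table. SAP 6.1 also promises frequencies and percentages for all categorical measures. Individual titers reach the final report through Listing 14, samples are taken at both visits, and the trial tests no formal hypothesis.

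Much of this stands as mitigation. No data are lost, and the protocol does commit to the estimate. But that commitment is what the SAP fails to carry through. A table limited to selected visits should include the endpoint visit. The general sentence in SAP 6.1 supplies neither an interval nor a Day 29 post-dose-2 output, and Listing 14 is unavailable at the Day 57 analysis.

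Two side points deserve care. First, Protocol 9.4.3 lists LNI as exploratory work that may be done, but SAP 9.2 plans it firmly. The dependence of Tables 32 and 33 on LNI therefore bites only if that assay is dropped or incomplete. Second, the endpoint statements do not themselves ask for two populations; the doubling to 12 comes from the SAP's practice of showing FA and PP. The choice of interval method is secondary to the visit mismatch.

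**Conclusion.** The concern holds. Followed as drawn, the SAP shells report post-dose-2 seroconversion at Day 57 instead of the endpoint visit. None of the 33 table shells gives the PRNT50 rate with an interval by treatment group at either endpoint visit. That conclusion assumes the shells are built as shown. Repeating Tables 32 and 33 by arm would supply the groups but not the Day 29 post-dose-2 row or the interval on the PRNT50 margin.

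The consequence is confined to estimation and reporting of a secondary endpoint. The documents give no basis for saying how different the Day 29 and Day 57 rates would be. It should be fixed before unblinding, since in a descriptive trial of this size the estimates are the result.

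**What to change.** - **Protocol 9.4.3:** change the post-dose-2 visit in the tabulation sentence to Day 29. Day 57 may stay if labelled as supportive.
- **SAP Tables 32 and 33:** add a Day 29 post-dose-2 row and state whether dose in the titles means dose level or dose number.
- **New SAP table, for FA and PP:** PRNT50 seroconversion without reference to LNI, giving n/N, percentage and a named exact 95% interval (Blaker or Clopper-Pearson) for 1 mcg, 5 mcg and placebo at Day 29 after each dose. Schedule it for the Day 57 analysis.

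The cost is one corrected protocol sentence, one added row in two shells and one new shell in two populations. No new visit, assay or subject is needed.
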